2.3 Sample size

At a power level of 0.9, with a 2-sided significance of 5%, a clinically relevant 0.12 unit change in pulsatility index (equivalent to a ~20% difference in risk of recurrent stroke), and conservatively allowing for a standard deviation of differences in PI between repeated measures of 0.2, gives an estimated minimum sample size of 32 patients (paired t-test). Allowing for a 15% drop-out rate, 38 patients would be required. A sample size of 66 achieves 90% power to detect the non-inferiority of sildenafil c.f. cilostazol using a non-inferiority margin of 0.08 (and mean of paired differences 0) at $\alpha=0.025$ (for a 95% CI) with a within-subject variance of 0.02. This equates to 75 patients in total with a 12% drop out rate.

2.4 Statistical interim analyses, data review and stopping guidelines

The DSMB will review recruitment and safety data after 30 patients have been recruited to the study or 12 months after the first visit of the first patient (whichever is sooner) or at the request of the sponsor or CI. Data will be reviewed in a blinded form, except where significant SAEs (in the opinion of the DSMB) or a potentially important number of severe AEs have occurred, when the data will be unblinded upon the request of the DSMB. No efficacy or futility interim analysis is planned.

If after 12 months recruitment falls below the rate expected to complete the study in 3 years, allowing for delays due to the COVID-19 outbreak, the overall study size can be reduced to 50 participants. Any data collected to that date, including on cilostazol, will be retained and analysed according to the original study plan.

The proportion of total within-patient SAEs of any grade occurring until the end of the relevant wash out period or 30 days after taking the last tablet (whichever is greater) will be compared between a) sildenafil vs placebo and b) cilostazol vs placebo using McNemar's test. "Statistically significant excess" is defined as a statistically significant result at the 5% level i.e. a test with a p-value<0.05. Any statistically significant excess of SAEs in the treatment arm, or occurrence of unexpected treatment-related SAEs of sufficient severity (in the view of the DSMB), may result in early cessation of the study. The DSMB will review the total number of SAEs and AEs on a yearly basis, and the Chair of the DSMB will be informed of any SAEs that occur within 15 days of the event.

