2. SYNOPSIS

Study Title	Oxford Haemodynamic Adaptation to Reduce Pulsatility: Randomised, placebo controlled, crossover study of effects of sildenafil on cerebral arterial pulsatility in patients with cryptogenic or lacunar stroke and small vessel disease
Internal ref. no. (or short title)	OxHARP
Study Design	Randomised, placebo-controlled, double-blind, crossover study

Study Participants	Cryptogenic or lacunar stroke or TIA, with mild to moderate small vessel disease changes on MRI or CT	
Planned Sample Size	75	
Treatment duration	3 weeks per treatment (12-14 weeks in total)	
Follow up duration	11 to 15 weeks	
Planned Study Period	36 months	
	Objectives	Outcome Measures
Primary	Assess whether 3 weeks of treatment with sildenafil (a PDE5 inhibitor) reduces cerebral arterial pulsatility on transcranial ultrasound, compared to placebo in patients with chronic vascular injury to the brain (small vessel disease)	Gosling's MCA pulsatility index on Transcranial ultrasound (MCA-PI)
Secondary	1) Assess whether 3 weeks of treatment with sildenafil (a PDE5 inhibitor) alters cerebral arterial reactivity to carbon dioxide on transcranial ultrasound, compared to placebo 2) Assess whether 3 weeks of treatment with sildenafil (a PDE5 inhibitor) has non-inferior effects on cerebral arterial pulsatility and reactivity to carbon dioxide on transcranial ultrasound, compared to cilostazol (a PDE 3 inhibitor)	1) and 2) Change in mean flow velocity on TCD before vs during CO2 challenge
Tertiary Objectives 1) Assess whether 3 weeks of treatment with sildenafil or cilostazol increases cerebral arterial reactivity to carbon dioxide on MRI, compared to placebo 2) Biochemical / genetic predictors of response to treatment	Reactivity of BOLD signal on MRI to CO2 challenge Markers of endothelial function (e.g. ICAM, VEGF, vWF) and genetic targets of the medications in the trial	After 3 weeks of treatment with sildenafil and cilostazol versus placebo Analysed in the 2 years after the last visit of the last participant.

Investigational Medicinal Product(s)	Sildenafil Cilostazol
Formulation, Dose, Route of Administration	Sildenafil: Oral 25 - 50mg tds, tablet Cilostazol: Oral, 50 - 100mg, BD, tablet (with mid-day placebo) Placebo: Oral, TDS

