10.4. Reporting Procedures for Serious Adverse Events

SAEs will be recorded and deemed reportable for up to 30 days following last administration of a trial drug, whether occurring after the end of the trial or between trial phases following a prolonged washout period.

All SAEs (other than those defined in the protocol as not requiring reporting) must be reported on the SAE reporting form to the DSMB within 24 hours of the Site Study Team becoming aware of the event. It will also be reviewed at the next DSMB meeting. Additional and further requested information (follow-up or corrections to the original case) will be detailed on a new SAE Report Form and emailed to the DSMB as requested. The DSMB will review all AEs and SAEs on a yearly basis.

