 - g) Alternative estimates of CVR (change in mean flow velocity per unit change in etCO₂) determined during hyperventilation, 4% CO₂ and 6% CO₂, each versus air.

2. Trial design

OxHARP is a randomised, placebo and actively controlled, three-arm double-blind (patient and clinician), assessor-blinded crossover trial. Using random allocation, participants will have three weeks of treatment with each of the following: sildenafil (25mg TDS, titrated to 50mg TDS after one week), placebo (one tablet TDS, titrated to 2 tablets after one week), cilostazol (50mg BD, titrated to 100mg BD after one week, with midday placebo). Following each treatment period, participants will undergo a clinical and physiological assessment, followed by at least one week washout before starting the next treatment. A subgroup of participants will undergo MRI imaging following sildenafil and placebo treatments to assess arterial pulsatility on MRI and cerebrovascular reactivity, and a further subgroup will undergo MRI on all three treatments. The primary objective will be assessed using a superiority hypothesis testing framework and a non-inferiority framework will be used for the secondary objective.

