2.6 Timing of outcome assessments

The outcomes will be assessed after completion of each treatment regimen (approximately day 28, day 56, day 84). Participants who are unable to attend an on-treatment study visit once their medication has been started (for example due to the COVID-19 pandemic) will be able to restart treatment at the point of stopping treatment if still during the titration phase but otherwise will restart the three weeks of treatment. The washout period can be prolonged as long as is necessary during the COVID-19 outbreak before the next treatment phase is started. If patients experience adverse effects of treatment requiring early cessation of treatment, an early physiological assessment will be offered if possible. All outcomes will be included in the intention to treat analyses, and in per protocol analyses if more than 1 week of treatment has been given, including a dose in the last 24 hours.

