5.4 Protocol pre-specified tertiary/exploratory analyses

The imaging analysis is specified in the protocol and this document. This will be completed and followed by the CI and relevant team members. Blood will be stored and then analysed at completion of the study, as the extent of testing will depend upon the demonstrated effect of medications in the study, whilst allowing for assessment of new biochemical and genetic markers reported during the study. Analysis of the markers of endothelial function and genetic targets of the trial medications (to be analysed in the two years after the last visit of the last participant) will also be detailed separately.

6. Safety data

Safety data will be routinely collected at each follow-up, including clinical history of side effects or adverse events, clinical examination and blood tests (FBC, U+Es, LFTs). The safety population will be used to summarise the adverse event data.

Adverse events (AEs) will be presented in tabular form a) per participant (see e.g. Table 6.1 below; all patients taking at least one tablet will be included) and b) per treatment administered in each period (e.g. see Table 6.2 below) including the wash-out (to a maximum of 30 days since the last tablet was taken). For each treatment within each patient, only the maximum severity of each type of AE will be displayed.

Table 6.1 Example of AE table

Adverse event (AE)		No. of participants	No. of AEs
e.g. Headache	No AE under any of the three treatments		
	No AE under sildenafil or cilostazol but AEs observed under placebo		
	No AE under sildenafil but AEs observed under placebo and cilostazol		

	AE observed under sildenafil but not under cilostazol or placebo		
	AE observed under sildenafil and cilostazol but not placebo		
	AE observed under sildenafil, cilostazol and placebo		

Table 6.2 Example of AE table

Period	Treatment	No. of participants taking treatment	No. of mild AEs	No. of moderate AEs	No. of severe AEs
First	Sildenafil				
	Cilostazol				
	Placebo				
Second	Sildenafil				
	Cilostazol				
	Placebo				
Third	Sildenafil				
	Cilostazol				
	Placebo				

SAEs are reportable for up to 30 days following the last administration of a trial drug whether after the end of a trial or between trial phases following a prolonged washout period and will be listed in full.

7. Statistical software

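### The SAE window in SAP 2.4 runs into the next treatment at the planned washouts, so one SAE can count against two drugs and McNemar's test is biased toward no excess

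*SAP*

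**What the plan says.** SAP section 2.4 compares SAEs within patients by McNemar's test. Each treatment's SAEs are those "occurring until the end of the relevant wash out period or 30 days after taking the last tablet (whichever is greater"), and the proportions "will be compared between a) sildenafil vs placebo and b) cilostazol vs placebo". A p-value below 0.05 defines a significant excess, and such an excess may end the study early.

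The washout is short by design. In SAP section 2 each assessment is "followed by at least one week washout before starting the next treatment". SAP 2.6 puts the assessments at "approximately day 28, day 56, day 84", and the protocol synopsis gives treatment duration as "3 weeks per treatment (12-14 weeks in total") and follow-up as 11 to 15 weeks. The washout may also be prolonged without limit because of the pandemic.

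Two other passages set a time limit. Protocol 10.4: "SAEs will be recorded and deemed reportable for up to 30 days following last administration of a trial drug". SAP section 6 tabulates AEs for each treatment "including the wash-out (to a maximum of 30 days since the last tablet was taken").

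No passage ends the 2.4 window at the first dose of the next drug, or says which treatment takes an SAE that falls in two windows.

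**The concern.** Section 2.4 takes the larger of the two limits, where section 6 takes the smaller. Whenever the washout is under 30 days, the 2.4 window extends into the next treatment period. An SAE in that stretch is charged to the drug being taken and to the drug before it.

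McNemar's test uses only discordant patients, that is, those with an SAE under one treatment and none under the other. If sildenafil follows placebo and the sildenafil SAE is charged to both, the patient becomes concordant and is lost to the test. This comparison is the plan's only statistical safety trigger, and the error lowers its chance of showing a real excess.

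When the washout exceeds 30 days the mismatch reverses: the 2.4 window runs past the 30-day SAE period in Protocol 10.4.

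**Working it through.** The plan gives no SAE rate, power or sample size for this test, so there is no figure of its own to reproduce.

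**1. Planned washout.** Treatment takes 3 × 21 = 63 days, and there are two washouts.
- Visits 28 days apart: 28 − 21 = 7 days.
- 12–14 weeks in total: (84 − 63)/2 = 10.5 to (98 − 63)/2 = 17.5 days.
- 11–15 weeks of follow-up: (77 − 63)/2 = 7 to (105 − 63)/2 = 21 days.

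**2. Overlap.** For washout *w*, the days on the next drug inside the previous drug's window are min(21, max(0, 30 − *w*)).

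| Washout (days) | 7–9 | 10 | 14 | 17 | 21 | ≥30 |
|---|---|---|---|---|---|---|
| Overlap (of 21 days) | 21 | 20 | 16 | 13 | 9 | 0 |

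**3. Direction.** Let *s*, *p* and *c* be the SAE risks on sildenafil, placebo and cilostazol. In the protocol's six sequences each drug is followed by each of the others in two, and is last in two. With full overlap and balanced sequences:
- charged to sildenafil: *s* + *p*/3 + *c*/3
- charged to placebo: *p* + *s*/3 + *c*/3
- difference: (*s* − *p*) × 2/3

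The cilostazol term cancels in expectation but adds discordant pairs, which is noise. The two-thirds factor needs no assumed SAE rate.

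**4. Discordant pairs.** Assume risks of 15% on sildenafil and 2% on placebo and cilostazol, with 75 patients.
- Single counting: sildenafil-only 75 × 0.15 × 0.98 = 11.0; placebo-only 75 × 0.02 × 0.85 = 1.3.
- SAP window at 7 days: the probability of sildenafil-only is 0.1441 (S-P-C), 0.1637 (S-C-P), 0.1470 (C-S-P), 0 (C-P-S), 0.0167 (P-S-C) and 0.1441 (P-C-S). The mean is 0.1026, or 7.7 patients. Placebo-only stays at 1.3.

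The 0.0167 in P-S-C comes from cilostazol SAEs, so in the two sequences with sildenafil directly after placebo no sildenafil SAE counts as excess.

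**5. Power.** This is the chance that an exact two-sided McNemar test gives p < 0.05 in the direction of excess. SAE times are uniform over the 21 treatment days, and patients fall into the six sequences with equal probability. The third drug has 2% risk unless stated. At least six discordant patients, all one way, are needed (five give p = 0.0625, six give 0.031).

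| n | Sildenafil vs placebo risk | Counted once | SAP, 7 days | 14 days | 21 days |
|---|---|---|---|---|---|
| 66 | 15% vs 2% | 0.71 | 0.39 | 0.48 | 0.59 |
| 75 | 15% vs 2% | 0.78 | 0.47 | 0.56 | 0.67 |
| 75 | 10% vs 2% | 0.41 | 0.18 | 0.24 | 0.31 |
| 75 | 5% vs 2% | 0.05 | 0.02 | 0.03 | 0.04 |
| 30 | 15% vs 2% | 0.19 | 0.05 | 0.08 | 0.12 |
| 30 | 10% vs 2% | 0.04 | 0.01 | 0.02 | 0.03 |

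At n = 66 and 15% vs 2%, a 17-day washout gives 0.53, and at 30 days there is no loss. If cilostazol also carries 15% risk (n = 75, 7 days), expected discordant pairs go from 11.0 vs 1.3 to 9.9 vs 3.9, and power from 0.78 to 0.27.

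**The case against.** The strongest objections, and what stands of each:

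- **Double counting is inferred.** The SAP never says that one SAE counts twice, and the 30-day limb could refer to the trial's final tablet, since period 3 has no following washout. That reading does not fit the text: the washout is the relevant one, and the greater of the two limits applies, so the window is per treatment. The missing attribution rule is a fact on either reading.
- **The large losses are at n = 66–75, when little is left to stop.** This stands in part. At the dated DSMB review (30 recruited or 12 months, whichever is sooner) not every patient will have completed both treatments, and the test rarely fires under either rule. Yearly reviews allow looks in between.
- **SAE risks of 10–15% in three weeks are high.** This stands: they are assumptions, and Protocol 8.4 describes the medication risk as low. At 5% vs 2% there is almost no power to lose. The overlap and the two-thirds factor do not depend on the rate.
- **The DSMB does not rely on this p-value.** This stands. SAEs reach it within 24 hours under Protocol 10.4, and under SAP 2.4 "occurrence of unexpected treatment-related SAEs of sufficient severity (in the view of the DSMB), may result in early cessation of the study".
- **Single counting gives unequal windows.** At a 7-day washout, periods 1 and 2 run 21 + 7 = 28 days and period 3 runs 21 + 30 = 51, against 51 throughout under the SAP. True, but it balances across drugs in expectation. Adding off-drug SAEs at the placebo rate (n = 66, 15% vs 2%) still gives 0.62 against about 0.33.
- **SAEs after day 30 need not be lost.** Correct: Protocol 10.3 records all AEs during the study. For long washouts the issue is inconsistent definitions rather than missing data.

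**Conclusion.** The concern holds and should be fixed. Read as written, the 2.4 window overlaps the next treatment throughout the planned range of washouts: fully at 7 days and for 9 of 21 days at 21. The effect on the sildenafil–placebo comparison is dilution, to two thirds of the true difference with full overlap and balanced sequences; cilostazol–placebo shrinks in the same way.

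The size of the power loss rests on assumed SAE risks, SAE times uniform over treatment, and a common washout length. It is substantial at risks of 10–15% with 66–75 patients. It is of little practical weight at 5%, or at the 30-patient review, where the test is weak anyway. It disappears once washouts reach 30 days. Because the DSMB has other grounds for acting, this is a defect in one safeguard and not a failure of safety oversight. Sections 2.4 and 6 of the SAP need reconciling whatever the SAE rate.

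**What to change.** In SAP 2.4, for the McNemar comparison, replace the window with: *each SAE is counted once, against the treatment most recently started, from its first tablet until the first tablet of the next treatment or 30 days after its last tablet, whichever comes first.* Add: *SAEs will also be listed by treatment under the full 30-day window as a sensitivity display.* This brings 2.4 into line with section 6. The 30-day SAE reporting period stays as it is.

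The cost is one phrase and one listing, with no change to data collection or reporting. The drawback is that a delayed SAE from the earlier drug is charged to the later one. Assuming 75 patients, 15% vs 2% and a 7-day washout:

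| Share of SAEs surfacing in the next treatment | Fix | SAP window |
|---|---|---|
| 10% | 0.67 | 0.45 |
| 20% | 0.55 | 0.43 |
| 30% | 0.43 | 0.42 |
| 35% | 0.36 | 0.40 |

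The two rules break even at about 30% delayed, which is why the sensitivity listing is needed.

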6. STUDY DESIGN

This is an investigator-led, randomised, placebo and actively controlled, double-blind (patient and clinician), assessor-blinded, crossover design study. 75 participants will be consented and assessed at a baseline visit, undergo a clinical assessment, followed by a research assessment including transcranial ultrasound to determine cerebral arterial pulsatility and reactivity. They receive three treatments in

randomised sequence: placebo (one tablet TDS, titrated to 2 tablets after 1 week), cilostazol (50mg bd, titrated to 100mg bd, with midday placebo) or sildenafil (25mg tds, titrated to 50mg tds)- NB titration up only happens if the participant is not on omeprazole. After each treatment, the will undergo a repeat clinical and physiological assessment, followed by at least 1 week washout before starting the next treatment. However, the washout may be prolonged if unavoidable (ie due to the COVID-19 pandemic). A subgroup of 60 participants will undergo MRI imaging when on sildenafil and placebo to assess arterial pulsatility on MRI and cerebrovascular reactivity, whilst 30 will undergo MRI on all three treatments.

FLOWCHART

Sequence	Drug 1	Drug 2	Drug 3
1	Sildenafil	Placebo	Cilostazol

2	Sildenafil	Cilostazol	Placebo
3	Cilostazol	Sildenafil	Placebo
4	Cilostazol	Placebo	Sildenafil
5	Placebo	Sildenafil	Cilostazol
6	Placebo	Cilostazol	Sildenafil

[figure not shown]
Screening phone-call ,patient invited and PIS sent in advance

Screening Visit:
Review eligibility
Detailed explanation of trial

CONSENT

Medical History & Examination
Blood tests / Pregnancy Test / ECG
Review medical records (if necessary)

Drug Allocation

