8.4. Randomisation, blinding and code-breaking

Randomisation will be performed by the Huddersfield PMU at the point of overencapsulation of medication in advance of provision of treatments to the Oxford Clinical Trial pharmacy. Study numbers will then be provided in sequence to participants at the Oxford Clinical Trial pharmacy. Each sequential study ID will be randomly allocated to one of six different treatment schedules, as outlined in the drug allocation

table on page 11, to produce three groups of 12 and three groups of 13 patients. The randomisation schedule will be generated by Huddersfield PMU.

The study will be blinded to the participant, blinded to the core study team ([name], [name], [name]) and blinded to the endpoint assessors (TCD measurement and MRI analysis). In patients consenting to the MRI substudy, the Trials pharmacy (or [name], who is otherwise independent of the study), will identify the visit at which the participant will be taking cilostazol so that the MRI scans can be arranged, but will not inform the patient or core team when sildenafil or placebo are assigned.

If clinical need requires unblinding of a specific patient, this will be done by the study pharmacist who will retain the randomisation schedule, following formal discussion with the Chief Investigator. Due to the low risk level associated with the study medication, and no specific medical intervention indicated for any potential complication that requires prior knowledge of current study treatment, emergency out of hours code-breaking is not required.

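### The SAE window for the McNemar stopping test (SAP 2.4) runs through the next treatment, so up to a third of on-treatment drug-caused SAEs also count against placebo and drop out of the test

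*SAP*

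**What the plan says.** SAP 2.4 compares the proportion of participants with SAEs between sildenafil and placebo, and between cilostazol and placebo, by McNemar's test at the 5% level. SAEs count "until the end of the relevant wash out period or 30 days after taking the last tablet (whichever is greater". A significant excess "may result in early cessation of the study".

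The schedule is three weeks per treatment, "followed by at least 1 week washout before starting the next treatment" (Protocol 6). SAP 2.6 confirms 28-day cycles: "The outcomes will be assessed after completion of each treatment regimen (approximately day 28, day 56, day 84". It also allows long gaps: "The washout period can be prolonged as long as is necessary during the COVID-19 outbreak before the next treatment phase is started".

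Two other places use 30 days as an upper limit. The SAP 6 tables assign adverse events to a treatment "including the wash-out (to a maximum of 30 days since the last tablet was taken". Protocol 10.4 states: "SAEs will be recorded and deemed reportable for up to 30 days following last administration of a trial drug".

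SAP 2.4 has no rule for an SAE that falls inside two treatments' windows.

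**The concern.** McNemar's test uses only participants who have an SAE under one treatment and not under the other. If the placebo window runs into the sildenafil period that follows it, an SAE caused by sildenafil is recorded under both. The participant becomes a concordant pair and contributes nothing. The safety test then loses sensitivity on the schedule most participants are meant to follow.

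The SAP 6 tables cap the window where SAP 2.4 extends it, so the stopping test and the safety tables could attribute the same event to different treatments.

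**Working it through.** The plan gives no overlap figure or SAE rate, so there is no figure of its own to reproduce. The overlap follows from the schedule alone. The detection probabilities need assumed rates.

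**Inputs**
- Treatment length: 21 days (SAP 2).
- Washout: at least 7 days. The 11 to 15 weeks of follow-up in the Protocol synopsis imply (77 − 63)/2 = 7 to (105 − 63)/2 = 21 days per washout.
- Sequences (Protocol 6): placebo directly precedes sildenafil in 4 and 5, and cilostazol in 1 and 6, so 2/6 for each drug.
- Sequence sizes: randomisation is "to produce three groups of 12 and three groups of 13 patients" (Protocol 8.4), so two sequences hold 24 to 26 of 75 participants (32.0% to 34.7%).

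**Overlap, no rates assumed.** Days of the next treatment inside the previous window = min(21, 30 − washout), or zero from a 30-day washout. Share of on-treatment drug SAEs also counted under placebo = 2/6 × overlap/21.

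| Washout (days) | Overlap (days) | Share lost |
|---|---|---|
| 7 to 9 | 21 | 33% |
| 14 | 16 | 25% |
| 21 | 9 | 14% |
| 30 or more | 0 | 0% |

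At 7 days the window extends 30 − 7 = 23 days past the next first dose.

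**Events needed.** In the exact two-sided test, five discordant pairs all one way give p = 2 × 0.5⁵ = 0.0625 and six give 2 × 0.5⁶ = 0.031, so six are needed. With a third lost, 6/(2/3) = 9 affected participants are needed on average. SAP 2.4 does not say which form of the test applies. The uncorrected chi-square form needs four pairs ((4 − 0)²/4 = 4, p = 0.046), hence 4/(2/3) = 6 participants.

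**Hand check without background SAEs.** Assume sildenafil causes an SAE in 13% of participants. The chance of at least six discordant pairs is P(Bin(N, 0.13 × 2/3) ≥ 6) under SAP 2.4 and P(Bin(N, 0.13) ≥ 6) without overlap:
- N = 75: 64% against 94%.
- N = 50: 26% against 65%.
- N = 30: 4% against 19%.

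**With background SAEs.** A simulation assumed 0.1 to 0.2 background SAEs per person-year, 7-day washouts, drug-caused SAEs spread evenly over the 21 treatment days, windows starting at first dose, all participants finished, and the exact two-sided test. Chance of flagging a sildenafil excess:

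| Excess, N | SAP 2.4 | Window ends at next first dose |
|---|---|---|
| 13%, 75 | 46–55% | 78–86% |
| 13%, 50 | 22–24% | 51–57% |
| 13%, 30 | 4–5% | 18–19% |
| 10%, 75 | 28–33% | 57–66% |
| 5%, 75 | 5–6% | 16–17% |

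At 13% and N = 75, 14-day washouts give 53–62% against 76–84%, and 21-day washouts 63–73% against 75–83%. If cilostazol also causes SAEs in 13%, its events spill into placebo and sildenafil windows too: below 30% against more than 75%.

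**Form of the test.** With assumed risks of 15% on sildenafil and 2% on each other treatment, the exact test at N = 30 falls from 19% to 5% and the uncorrected chi-square form from 45% to 25%. At N = 75 they fall from 79% to 50% and from 85% to 64%.

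**Prolonged washouts.** Beyond 30 days the overlap disappears, but the SAP 2.4 window then has no upper limit and outruns the 30-day SAE reporting period. If 10% of washouts last 180 days, capping the window at 30 days gains only 2 to 4 points at N = 75 and nothing at N = 30.

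**The case against.** **Double counting is inferred.** SAP 2.4 does not say to count an SAE twice, and an analyst might use the washout for periods 1 and 2 and 30 days only after period 3. But choosing the greater of the two limits rules that reading out for any washout under 30 days, and nothing else in the plan assigns the event to one treatment.

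**The conflicts are narrow.** This partly stands. The SAP 6 cap governs the adverse event tables, while SAEs are listed in full. Protocol 10.4 departs from SAP 2.4 only when a washout exceeds 30 days.

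**The sample sizes and excess rates flatter the point.** At N = 75 with everyone finished there is nothing left to stop. The scheduled review is at 30 recruited or 12 months, where the exact test rarely flags under either window. An excess of 10 to 13% within three weeks has no support in the documents, which describe low-risk drugs, and at 5% the test is poor either way. All of this stands. The gap matters most at a later yearly review, or at the 50 participants to which the trial may be reduced. The fraction lost does not depend on any assumed rate.

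**One third is a ceiling.** This is correct. It requires washouts of 9 days or less and SAEs that arise on treatment. If SAEs were spread over treatment and the drug's own 7-day washout, the share would be 23/28 × 1/3 = 27%. A longer window would also catch delayed events, which the simulation does not credit.

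**Consequences are limited.** The rule is advisory, the DSMB receives SAEs by other routes and can unblind, and efficacy results are unaffected. This also stands, and it limits the seriousness of the point without removing it.

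**Conclusion.** The concern holds. As written, the SAP 2.4 window makes the stopping test count one event against both treatments it compares. The loss is one third of participants with an on-treatment drug-caused SAE at washouts up to 9 days, shrinking to none at 30 days. That figure rests only on the schedule and the six sequences. The detection probabilities rest on assumed SAE rates and, except where stated, on the exact test, so they illustrate size only.

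Randomised order means neither drug is favoured, but it does not prevent the dilution. This should be corrected, although it does not threaten the trial's main conclusions. The mismatch with Protocol 10.4 is a minor supporting point.

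**What to change.** In SAP 2.4, count SAEs from first dose to the earlier of 30 days after the last tablet or the first dose of the next treatment. Assign each SAE to one treatment only and list later SAEs separately for the DSMB. This matches the window of the SAP 6 adverse event tables and removes the overlap at any washout length. It would also help to state which form of McNemar's test applies.

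The cost is one clause and no new data. On the standard schedule, treatments 1 and 2 get 21 + 7 = 28 days and treatment 3 gets 21 + 30 = 51 days, an inequality that random order balances between drugs. A delayed SAE that occurs after the next first dose would be attributed to the next treatment or left to the listing.

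If equal windows are preferred, use last tablet plus 7 days for all three treatments (28 days each). Under the same assumptions (N = 75, 13% excess) this flags 81–87%, at least as good as the earlier-of window, but leaves SAEs after day 7 to the separate listing.
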